## SUMMARY

[figure not shown]
Title	Key Performance Indicators for the assessment of diagnostic and therapeutic pathway of NSCLC patients: a multicenter study (KIND NSCLC)
Protocol Code	IRST 162.13
Acronym	KIND NSCLC
Rationale	
Lung cancer is the most common cancer diagnosed globally and the leading cause of cancer death worldwide. Non-Small Cell Lung Cancer (NSCLC) accounts for approximately 85% to 90% of all lung cancer with 5-year survival rate of 22.1%. Approximately 79% of NSCLC patients are diagnosed at advanced stage (IIIB or IV) NSCLC. Furthermore, recurrence rates after complete surgical resection range from 30% to 75% among patients initially diagnosed with stage I, II, or III, with the majority of patients who experiencing metastatic recurrence.
 
However, significant advanced in testing and treatment have been made in recent years with the potential to positively impact lung cancer outcomes. These include rapid positive progress in the use of

[figure not shown]
immunotherapy, which has become an important therapeutic alternative influencing the clinical approach and becoming the first choice of treatment in many cases of advanced NSCLC. Moreover treatment of NSCLC is highly complex, resulting in wide variations in the patterns of care. An appropriate care of patients with NSCLC requires managerial skills merged with clinical knowledge and experience, and coordination among multidisciplinary specialists. Nevertheless, to date the management of patients with NSCLC is characterized by a sequence of medical investigations and visits of various specialists, whose timeframes are often not short, whose assessment is fragmentary, poorly coordinated and often followed by inappropriate decisions. The organizational framework described above makes the analysis of NSCLC particularly interesting.

Currently, there is an increasing interest in the use of administrative healthcare databases in clinical and health services research as they provide timely and easy access to a large source of information regarding subjects in a defined geographical area. Administrative data have been widely used in different types of epidemiologic research, health services, and outcomes cancer research. The investigated population can be identified through disease-specific codes, prescriptions and disease-specific procedure codes among administrative databases.

[figure not shown]
In light of the rapid change of NSCLC therapeutic options, we are proposing a non-interventional study to generate real-life practice data on NSCLC patient from administrative databases. The focus of this study is to allow a deeper knowledge about the quality of NSCLC care pathway in three hospital of Emilia-Romagna region, monitoring the routinely clinical practice patterns through the measurement of key performance indicators (KPIs). Data will be entirely collected from administrative databases.

	
This study can help to define best clinical practice and to understand the management of resources for NSCLC patients, through a fast and cheap approach, much reflective of the real world.

Study Design	
This is a multicenter, observational study involving a retrospective collection of data. A total of potential 16 key performance indicators (KPIs) had been developed from a panel of experts (clinicians, IT experts, etc..) to investigate the appropriateness of care in NSCLC patients, with a special focus on the use of immunotherapy. The eligible population and data will be gathered retrospectively using an algorithm. Administrative databases will be used as unique resource:
 

• to identify target population;

• to collect patient's data with which measure KPIs.

Study duration	
Enrollment period: from January 2017 to December 2017
 
Total duration of the study: 1 year from approval date of study by Ethics Committee.

Study Promoter	IRST
Study Centers	
This study is an Italian Multi-Center study. The participating sites are:
 

• Istituto Scientifico Romagnolo per lo Studio e la Cura dei Tumori (IRST-IRCCS);

• Department of Oncology and Hematology, Policlinico of Modena;

• Department of Oncology, Arcispedale S. Maria Nuova Reggio Emilia.

Objectives	
The project aims to measure a set of potential indicators (KPIs) derived from administrative databases in order to investigate the appropriateness and quality of NSCLC care among participating sites.
 
The secondary aim is to develop and validate an algorithm to identify the eligible population of the study from SDO ( hospital discharge

[figure not shown]

	card) against to a clinical database (only at IRST site).
Number of Subjects	About 400 patients are expected globally.
Diagnosis and Main Inclusion Criteria	

1. Patients identified through the algorithm as described at paragraph 4.1;

2. Male or female;

3. At least 18 years at date of first index hospitalization

Procedures and data collection	Patient information will be obtained only from administrative databases both for out-patient and in-patient settings.
Statistical Methodology	
For primary objective, for each indicator, the proportion of patients who receive the procedure, in the defined time window, among those eligible, will be calculated. Descriptive statistics as arithmetic mean and standard deviation (SD) as well as median and range value (maximum-minimum) will be presented for KPI related to average time. Two-sided 95% confidence interval (95% CI) will be reported as appropriate and specified for KPI expressed as proportion. For secondary objective, the validity of algorithm will be evaluated by individual matching among cases retrieved from administrative database and medical chart obtained from IRST.
 
Sensitivity, positive predictive value as well as specificity and negative predictive value will be calculated, and exact (Clopper-Pearson) 95% confidence limits for binomial distribution will be applied.

[figure not shown]
## ABBREVIATIONS

ADI	Assistenza domiciliare integrata
AFT	Assistenza farmaceutica territoriale
ASA	Assistenza ambulatoriale
CC	Coordinating Center
CI	Chief Investigator
CRF	Case Report Form
FED	Farmaci ad erogazione diretta
GCP	Good Clinical Practice
ICF	Informed Consent Form
ICH	International Conference of Harmonization
ICP	Integrated Care Pathway
IEC	Independent Ethics Committee
KPI	Key Performance Indicator
mNSCLC	Metastatic Non Small Cell Lung Cancer
NSCLC	Non Small Cell Lung Cancer
PI	Principal Investigator
REM	Registro mortalità regione Emilia Romagna
ASA	Assistenza ambulatoriale
SDHS-Hospice	Scheda di dimissione Hospice
SDO	Scheda di dimissione ospedaliera

[figure not shown]

## 1. BACKGROUND AND RATIONALE

Lung cancer is the most common cancer diagnosed globally and the leading cause of cancer death worldwide . Non-Small Cell Lung Cancer (NSCLC) accounts for approximately 85% to 90% of all lung cancer  with 5-year survival rate of 22.1% . Approximately seventy-nine percent (79%) of NSCLC patients are diagnosed with advanced (stage IIIB or IV) NSCLC . Furthermore, recurrence rates after complete surgical resection range from 30% to 75% among patients initially diagnosed with stage I, II, or III, with the majority experiencing metastatic recurrence .

However, significant advances in testing and treatment, which have the potential to positively impact lung cancer outcomes have been made in recent years. These include rapid progress in the use of immunotherapy, which has become an important therapeutic alternative influencing the clinical approach and becoming one of the main choices of treatment in many cases of advanced NSCLC. Moreover, treatment of NSCLC is highly complex, resulting in wide variations in the patterns of care. An appropriate care of patients with NSCLC requires managerial skills merged with clinical knowledge and experience, and coordination among multidisciplinary specialists . Therefore, to date the management of patients with NSCLC is characterized by a sequence of medical investigations and visits of various specialists, whose timeframes are often not short, and the risk of fragmentary assessments, poorly coordinated and often followed by inappropriate decisions, is high. The organizational framework described above makes the analysis of NSCLC care pathway particularly interesting. This objective could be pursued measuring some key performance indicators (KPIs) of care pathway in NSCLC. The measure of KPIs in NSCLC is not an easy task. Available literature on KPIs in NSCLC is relatively limited and there is no universal agreement on quality of care indicators. However, the employment of quality indicators is an important tool that can help to improve patient's care and outcomes, promote patients safety, increase patient satisfaction, and to optimize the use of resources.

Currently, there is an increasing interest in the use of administrative healthcare databases in clinical and health services research as they provide timely and easy access to a large source of information regarding subjects in a defined geographical area. Administrative data have been widely used in different types of epidemiologic research, health services, and outcomes cancer research .

Healthcare administrative databases were also used to identify study population through disease-specific codes, prescriptions or specific procedure codes.

In light of the recent introduction of immunotherapies, we are proposing a non-interventional study to generate real-life practice data on NSCLC care pathway. The focus of this study is to allow a deeper knowledge about the quality of NSCLC care in three hospitals of Emilia-Romagna region, monitoring the routinely clinical practice through the measurement of key performance indicators (KPIs). Data will be entirely collected from administrative databases.

This study can help to define best clinical practice and to understand the management of resources for NSCLC patients, through a fast and cheap approach, much reflective of the real world.

## **2. OBJECTIVES**

### ***2.1 Primary Objective***

[figure not shown]
To measure a set of potential indicators (KPIs) derived from administrative database in order to investigate the appropriateness and quality of NSCLC care among participating sites.

### ***2.2 Secondary Objectives***

The secondary aim is to develop and validate an algorithm to identify the eligible population of the study from administrative databases against to a clinical database (only at IRST site. Algorithm will be used to identify eligible patients and measure KPIs in the other two participating sites only through administrative database.

## **3. STUDY DESIGN**

This is a multi-center, observational study involving retrospective collection of NSCLC patients information. All consecutive patients who had a newly diagnosis of NSCLC in 2017 from healthcare administrative database and received at least one anti-cancer drug treatment between January 2017 and December 2017, identified through the proposed algorithm, will be considered. All data needed for KPI calculation, even if they fall outside January-December 2017 period, will be collected. The end of data collection will be defined as patient death or 30 June 2018, whichever came first.

A set of potential KPIs had been developed from a panel of experts (clinicians, IT experts etc..) to investigate the appropriateness of activities within NSCLC care pathway, with a special focus on the use of immunotherapy.

The eligible population and data will be gathered retrospectively through an algorithm from administrative databases (SDO, REM, ASA, FED, AFT, ADI, SDHS-hospice).

Administrative data will be used as unique resource:

- to identify patients cohort;
- to measure KPIs along care pathway ;

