34.6	SCARIFICATION OF PLEURA														
4	
Percentage of surgical patients on the total number of patients with exploratory thoracotomy in inpatient setting.            NUM: Total of patients with only exploratory thoracotomy procedure (Cod 34.02);            DEN: Number of surgical patients;            For major surgery, ICD-9-CM codes were selected as reported for KPI 3.            Surgical patients defined as patients who receive any surgical procedure (major and/or explorative)
														
5	
Percentage of patients undergoing neoadjuvant therapy ( CT or CT+RT within 6 months prior to the first major resection date)            NUM: Number of patients who underwent induction treatment as CT or CT+RT in the 6 months prior to surgery;            DEN: Total number of surgical patients;            The algorithm will not be able to identify patients who received neoadjuvant therapy in clinical trials.            For major surgery, ICD-9-CM codes were selected as reported for KPI 3.
														
6	
30-day mortality rate from major surgery            NUM : Number of patients who died within 30 days from major surgery;            DEN: Total number of surgical patients;            For major surgery, ICD-9-CM codes were selected as reported for KPI 3.
														
7	
Percentage of patients discussed in the multidisciplinary team (MDT) meeting at least once in the year of incidence            NUM: Number of patients discussed at least one time in MDT meetings;            DEN: Total number of patients identified by the algorithm;
														
8	
Percentage of patients who performed imaging exams such as MRI, TC and PET within 7 days from MDT meeting            NUM: Number of patients who performed imaging exams within 7 days from MDT meeting;            DEN : Total number of patients discussed in MDT meeting;
														
9	
Average and range of length of stay calculated as the mean difference among date of discharge and date of admission.
														
10	
Average time between biopsy and the first administration of systematic anti-cancer drug (excluded neoadjuvant patients of KPI 5) calculated as the average difference among biopsy and the first date of administration of chemotherapy.            For patients enrolled in experimental clinical trial will not be possible to retrieve information on therapies from administrative database.
														

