11	
KPIs on THERAPIES For patients enrolled in experimental clinical trial will not be possible to retrieve information on therapies from administrative database.
 
a) Percentage of patients treated with immunotherapies NUM: Patients with at least one administration of immunotherapy According to Anatomical Therapeutic Chemical Classification System ATC, the following codes will be investigated: L01XC17 nivolumab L01XC18 pembrolizumab L01XC32 atezolizumab
 
DEN: Total number of patients identified by the algorithm who underwent anti-cancer drug treatment for NSCLC, as single or double agent chemotherapy, target therapy etc..(excluded neoadjuvant patients of KPI 5)
 
b) Percentage of patients who underwent immunotherapy for more than 6 months after first dose. NUM: Number of patients who underwent immunotherapy more than 6 months after the first administration; DEN: Total number of patients identified by the algorithm who underwent immunotherapy;

12	
Percentage of patients who underwent anti-cancer drug treatment in the last 30 days of life NUM: Number of patients who underwent anti-cancer drug treatment in the last 30 days of life; DEN: Total number of patients identified by the algorithm who deceased

13	
Percentage of patients who underwent the first administration of systematic anti-cancer drug within 30 days from discussed in MDT meeting NUM: Number of patients who underwent first systematic anti-cancer drug administration within 30 days from MDT; DEN: Total number of patients patients identified by the algorithm discussed in MDT meeting;

14	
Percentage of patients who underwent RT in the last 30 days of life ( excluded palliative treatments single fraction) NUM: Number of patients who performed RT in the last 30 days of life ( excluded palliative treatments); DEN: Total number of patients identified by the algorithm who deceased;

15	
Percentage of patients who underwent at least one Integrated Home Care (IHC) NUM: Number of patients who underwent IHC service; DEN: Total number of patients identified by the algorithm;

16	
Percentage of patients who underwent at least one hospice care NUM: Number of patients who underwent hospice care; DEN: Total number of patients identified by the algorithm;

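### If the section 3 drug clause is applied, late-2017 patients enter only when treated quickly, so KPI 10 is biased down and KPI 13 up; sections 4.1, 4.3 and 7.1 carry no such clause

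*Protocol*

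**What the plan says.** Section 3 sets two joint conditions for entry. The first is the diagnosis: "All consecutive patients who had a newly diagnosis of NSCLC in 2017 from healthcare administrative database". The second is treatment: the patient must have "received at least one anti-cancer drug treatment between January 2017 and December 2017". Both windows close on 31 December 2017.

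Section 3 then widens data collection but not entry: "All data needed for KPI calculation, even if they fall outside January-December 2017 period, will be collected". It adds: "The end of data collection will be defined as patient death or 30 June 2018, whichever came first".

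Two indicators in section 5.2 measure the interval that the treatment condition restricts. KPI 10 is the "Average time between biopsy and the first administration of systematic anti-cancer drug", with neoadjuvant patients excluded. The numerator of KPI 13 is the "Number of patients who underwent first systematic anti-cancer drug administration within 30 days from MDT"; its denominator is every algorithm patient discussed by the MDT, treated or not.

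Other sections describe a different cohort. The algorithm criteria in 4.1, the inclusion criteria in 4.3 and the statistical population in 7.1 contain no requirement that a drug was given. Section 7.2 ties the expected 400 patients to 4.1. Section 5 limits the data for the primary objective to 2017, which conflicts with section 3.

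**The concern.** Under the section 3 clause, the time allowed for a first drug depends on the diagnosis date: about 12 months for a patient diagnosed in early January, a few days for one diagnosed in late December. Take two patients biopsied on 1 December 2017. One starts a drug on 20 December (19 days) and is kept. The other starts on 10 January 2018 (40 days) and is excluded, although the study would be collecting data until the end of June. Entry therefore depends on the quantity that KPI 10 averages and KPI 13 scores.

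The sentence on data outside 2017 does not cure this. It concerns data needed to calculate KPIs and does not change who is in the cohort.

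The study exists to describe quality of care at three sites, and waiting time to first drug is one of its main results. A rule that removes slow starters makes care look faster, and it removes more of them where delays are longer.

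**Working it through.** **Is there a figure to reproduce?** No. Section 7.2 states that no formal sample size was calculated, and the protocol gives no delay distribution. The check is therefore a truncation calculation under stated assumptions.

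**Inputs.** From section 3: diagnosis in 2017, drug by 31 December 2017, data to 30 June 2018. Assumed: diagnosis day D uniform on 0 to 365; delay T from diagnosis (taken as the biopsy date) to first drug, gamma or lognormal, among patients who are eventually treated.

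**Entry rules.** Section 3: D + T ≤ 365. Counting first doses to 30 June 2018: D + T ≤ 545.

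**Closed form** (T below 365 days, mean μ):
- share entering = 1 − μ/365
- mean among those entering = (365μ − E[T²]) / (365 − μ)

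Example, gamma with mean 45 and coefficient of variation (CV) 0.6:
- E[T²] = 45² × (1 + 0.36) = 2,754
- mean = (16,425 − 2,754) / 320 = 42.7 days
- share entering = 1 − 45/365 = 88%

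Simulation gives the same values. It was used for all cases because heavy tails pass 365 days.

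| Assumed delay (days) | Enter under section 3 | True mean | Mean under section 3 | Mean, doses to 30 June 2018 | Within 30 days: true, then section 3 |
|---|---|---|---|---|---|
| Gamma, mean 30, CV 0.6 | 92% | 30.0 | 29.0 | 30.0 | 58.0%, 60.1% |
| Gamma, mean 45, CV 0.6 | 88% | 45.0 | 42.7 | 45.0 | 33.5%, 36.2% |
| Gamma, mean 60, CV 0.6 | 84% | 60.0 | 55.8 | 59.9 | 20.4%, 23.1% |
| Gamma, mean 90, CV 0.6 | 75% | 90.0 | 79.4 | 88.6 | 9.1%, 11.4% |
| Gamma, mean 45, CV 1.0 | 88% | 45.0 | 38.7 | 44.5 | 48.7%, 53.5% |
| Gamma, mean 60, CV 1.0 | 84% | 60.0 | 48.4 | 58.0 | 39.4%, 45.3% |
| Lognormal, median 30, log-SD 0.6 | 90% | 35.9 | 34.2 | 35.9 | 49.9%, 52.4% |
| Lognormal, median 40, log-SD 0.8 | 85% | 55.1 | 46.9 | 53.3 | 35.9%, 40.1% |
| Lognormal, median 60, log-SD 0.8 | 78% | 82.6 | 64.6 | 76.1 | 19.3%, 23.4% |

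The shortfall in the mean runs from 30.0 − 29.0 = 1.0 day to 82.6 − 64.6 = 18.0 days. The excess in the 30-day share runs from 2.1 to 5.9 points. The loss is concentrated late in the year: with gamma mean 45 and CV 0.6, only 13% of December diagnoses enter, with a mean delay of 15.5 days.

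**KPI 13 as defined.** The table covers treated patients from diagnosis, whereas KPI 13 starts at the MDT meeting and keeps untreated patients in its denominator. Assume that 80% of MDT patients are ever treated, the MDT meets 14 days after diagnosis, and the delay from MDT to drug is gamma with mean 45 and CV 0.6:
- all MDT patients, as KPI 13 is written: 26.9%
- treated patients only, no truncation: 33.6% (+6.7 points)
- section 3 cohort: 36.4% (a further +2.8 points)

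In this case, dropping never-treated patients does more harm than the truncation.

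**The case against.** The strongest objection is that the clause may not be the operative rule. It appears only in section 3. Sections 4.1, 4.3 and 7.1 define the cohort without it, and KPI 11a restricts its own denominator to treated patients, which would be largely redundant if everyone had to be treated. This stands: if 4.1 governs, this bias does not arise. But nothing in the protocol ranks section 3 below 4.1, and reconciling the sections by adopting section 3's wording would build the truncation in.

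The second objection is size. With short, light-tailed delays the effect on KPI 10 is only 1 to 2 days; the larger figures depend on long delays that the protocol neither gives nor rules out. This also stands, so the size can be given only as a range.

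Three stronger readings are tempting and are not supported:
- A reader might apply the 15% loss in the lognormal median-40 case to the planned 400 and conclude that 60 patients would be lost. The 400 refers to the 4.1 population, where no drug is required, so that rate does not apply to it.
- A reader might take a rise from 36% to 40% as the bias in KPI 13. That comparison covers treated patients from diagnosis, which is not how KPI 13 is defined.
- A reader might infer that a per-patient window, such as a drug within 180 days of the index hospitalization, is the remedy. It fits the 30 June 2018 cut-off and improves the 30-day share, but it still selects on the KPI 10 interval. For lognormal median 40 it gives 48.8 days against a true 55.1, leaving (55.1 − 48.8) / (55.1 − 46.9) = 77% of the bias. For median 60 it gives 64.7, against 64.6 under section 3 and a true 82.6. It also keeps never-treated patients out of KPI 13.

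**Conclusion.** The point holds conditionally. Section 3 contradicts 4.1, 4.3 and 7.1 on whether a drug is needed for entry. If section 3 is followed, its calendar-year clause biases KPI 10 down and KPI 13 up. Those directions follow from the wording, provided some patients diagnosed in 2017 start a drug in 2018.

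The size rests on uniform diagnosis dates and assumed gamma or lognormal delays with means of about 30 to 90 days: about 1 to 18 days on the KPI 10 mean and about 2 to 6 points on the 30-day share among treated patients. KPI 13 moves further through the loss of never-treated MDT patients, by an amount that depends on the proportion never treated, which the protocol does not give.

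Deleting the clause is not enough if section 5's limit to 2017 data is left standing. First doses in 2018 would then go unrecorded. KPI 10 would be truncated in the same way, while KPI 13 would be biased down, because late-2017 MDT patients would stay in the denominator without a recorded dose.

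**What to change.** 1. In section 3, delete the condition "received at least one anti-cancer drug treatment between January 2017 and December 2017" together with the conjunction before it, so that the cohort is the 4.1 algorithm population diagnosed in 2017, in agreement with 4.3 and 7.1.
2. In section 5.2, apply a drug condition only in the KPIs that need it, such as KPI 10 and KPI 11a, and count first doses up to 30 June 2018.
3. Keep all MDT-discussed algorithm patients in the KPI 13 denominator, as its definition already reads.
4. Amend the sentence in section 5 that limits the data to 2017 so that it matches section 3.
5. Do not substitute a 180-day entry rule.

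The cost is a few sentences and, if the drug clause is already coded in the extraction, removing that filter; section 3 already plans to collect the data. Reported waiting times will look somewhat longer and the within-30-day percentage lower. Some truncation remains for delays running past 30 June 2018: at most about 2 days on the KPI 10 mean in eight of the nine cases above, and 82.6 − 76.1 = 6.5 days in the heaviest-tailed one. The 30-day share among treated patients returns to within about 0.5 points of its true value.
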